4. SUBJECT ELIGIBILITY

4.1 Inclusion Criteria:

- 1 Age 20-89 years
- 2 Women with a biopsy proven diagnosis of ductal carcinoma in situ or invasive carcinoma of the breast
- 3 Women must have undergone treatment for breast cancer, including one or more of the following: surgery, radiation therapy, chemotherapy, immunotherapy, or hormonal therapy. Women undergoing active chemotherapy or immunotherapy are not allowed on study.
- 4 Participants must have abstained from smoking for at least 12 months
- 5 Participants must be prescribed by their treating physician to engage in resistance training for 3 months (12 weeks).
- 6 Participants will be assessed 1 year following exercises as they were at baseline and post exercise as SOC.

4.2 Exclusion Criteria:

- 1 Any current treatment with chemotherapy for breast cancer
- 2 Inability to get and down off the ground or squat body weight
- 3 Inability to safely engage in group sessions
- 4 Severe arthritic, joint, cardiovascular, or musculoskeletal condition deemed by PI to be unsafe to engage in resistance training

4.3 Inclusion of Women and Minorities

Women of all races/ethnicities will be eligible for this study and accrual is expected to reflect the population of subjects seen within the Pittsburgh, PA area.

5. EXERCISE REGIMEN

5.1 Location:

The exercise facility participating in the study is located within AGH Suburban at the AHN Cancer Institute Exercise Oncology and Resiliency Center, [name].

5.2 Personnel:

As per SOC, the exercise regimens will be constructed and reviewed by the Exercise Oncology Consortium and monitored by [name], CSCS, and associated Certified Strength and Conditioning Specialists and staff. [name] is a radiation oncologist trained in integrative medicine and is a Certified Strength and Conditioning Specialist. Resistance training classes will be directly observed by [name] or his team of CSCS, and

regimens will be continually adjusted for both exercise progression and safety as per SOC at the facility.

5.3 Exercise Regimen:

The exercise regimen will utilize a mixture of compound movements utilizing both open and closed kinetic chain movements (CKC), focusing on exercises with the goal of improving body composition, strength, mobility, muscle mass, and several associated variables. CKC exercises are generally more intense as they require multi-joint movement patterns. Examples include lunges, squats, and deadlifts. Classes will be run by certified exercise and performance personnel and workouts will be directly observed and continually adjusted for both exercise progression and safety, as per SOC. It will follow a linear progression technique and guidelines from the National Strength and Conditioning Association (NSCA) will be followed. The observed classes will take place three times per week. Warm-up exercises focused on mobility, flexibility and core activation will be performed to increase mobility and reduce the risk of injury. Each individual exercise workout will generally progress from most intense, CKC, compound, and athletic movements to least intense throughout the workout to maximize safety. Additionally, each workout will provide full body resistance training to focus on functional exercises, intensity, and efficiency. Each workout will take approximately 45-60 minutes. When a participant has exceeded the goal number of repetitions by two for two consecutive weeks, the weight lifted will be increased via NSCA standards. The SOC total exercise regimen will last 3 months. The SOC follow up assessment will occur 1 year after exercise. Data from the SOC exercise and assessments will be used for research.

Exercise class attendance will be recorded. Workout regimens, including exercise type, sets, and repetitions will be recorded to aid in workout consistency and progression and to calculate load lifted. Initial strength assessment will occur during the initial two weeks of the workout regimen to help ascertain proper weight usage. Repetition schemes to mimic basic exercise principles for hypertrophy, strength, and power based on 1-repetition maximum (1RM) extrapolation and repetition range charts after assessing each exercise performed to near repetition fatigue/voluntary failure (i.e. when a repetition or safe lifting form can no longer be maintained while monitored by exercise physiologist).

Weight lifted, repetitions, sets, and notes will be recorded and utilized to estimate intensity via volume load calculations (volume load = weight lifted \times repetitions \times sets). An example of a workout is listed below.

Day One (anterior muscle closed-chain compound exercise focus):

A1: Split Squat 4X6 week 1-4, 4X4 weeks 5-8, 4X2 week 9-12

A2: Side plank 3X20 seconds each side week 1-6, 3X30 seconds each side week 7-12

B1: Bird dog row 3X10 week 1-6, 3x12 week 7-12

B2: Feet elevated glute bridge 3X10 week 1-6, 3x12 week 7-12

B3: Half Kneeling 1 arm overhead press 3X10 week 1-6, 3x12 week 7-12

Day Two (posterior muscle closed-chain compound exercise focus):

A1: Trap bar (or straight bar) Deadlift 4X6 week 1-4, 4X4 weeks 5-8, 4X2 week 9-12

A2: Band pull-aparts 3X10 week 1-6, 3x12 week 7-12

B1: Goblet squat 3X10 week 1-6, 3x12 week 7-12

B2: Incline bench press 3X10 week 1-6, 3x12 week 7-12

B3: Tall kneeling front raise 3X10 week 1-6, 3x12 week 7-12

Day Three (strength/hypertrophy focus):

A1: Bent over row 4X6 week 1-4, 4X4 weeks 5-8, 4X2 week 9-12

A2: Pushups (use bar to raise up height if needed) 3X10 week 1-6, 3x12 week 7-12

B1: Weighted hip bridge 3X10 week 1-6, 3x12 week 7-12

B2: Step ups 3X10 week 1-6, 3x12 week 7-12

B3: Farmers carries 3X10 steps each leg week 1-6, 3X12 steps each leg week 7-12

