The exercise program will last three months. The initial exercise schema was developed by the PI and exercise personnel. Throughout the exercise program, participants will continuously be assessed via load lifted calculations and observations of exercise mechanics, both of which will impact increases in load and exercise difficulty during the program, as per SOC.

6.4 Follow-up Period:

There will be no follow-up once an individual completes the study.

6.5 Early Withdrawal of Subject(s):

If at any time the constraints of this protocol are detrimental to the patient's health and/or the patient no longer wishes to continue in the study, the patient will be removed from the protocol follow-up. In this event the reason(s) for discontinuation of study participation will be noted by the PI in the record. Data acquired up until that point will be retained for analyses.

There will be a SOC follow up assessment 1 year after the completion of the exercise program. The data from the SOC assessment will be used for research purposes.

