APPENDIX III: Strength Assessment

Strength assessment will be performed and recorded for each exercise during the initial two weeks of the exercise program, known as the “run-in” period, as is SOC. These numbers will be recorded for each participant. Loads will be calculated at three weeks and then recalculated every

4 weeks until completion of the protocol. Load lifted will be calculated by multiplying the number or repetitions, weight per workout, and number of sets.

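### Volume load is described as an estimate of intensity, but it measures training volume and can fall while the weight lifted rises

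*Combined protocol and SAP*

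**What the plan says.** Section 5.3 has weight, repetitions and sets recorded and "utilized to estimate intensity via volume load calculations", with volume load defined as weight × repetitions × sets. It bases repetition schemes on extrapolation to a one-repetition maximum (1RM), "after assessing each exercise performed to near repetition fatigue/voluntary failure".

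The workout that follows is introduced with "An example of a workout is listed below". Its main lift on each day loses repetitions in blocks, for instance "A1: Split Squat 4X6 week 1-4, 4X4 weeks 5-8, 4X2 week 9-12". Most other lifts gain repetitions, for instance "B1: Goblet squat 3X10 week 1-6, 3x12 week 7-12". Section 5.2 adds that "regimens will be continually adjusted for both exercise progression and safety".

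Appendix III, headed Strength Assessment, states that "Strength assessment will be performed and recorded for each exercise during the initial two weeks of the exercise program". It then has loads calculated at three weeks and every four weeks after that, as repetitions × weight × sets, and gives no other calculation. Section 6.3 says that "participants will continuously be assessed via load lifted calculations and observations of exercise mechanics", and uses both to guide progression.

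Exploratory objective 3 (section 3.1) names strength and load lifted as two items. Grip strength is measured by dynamometer (section 6.2; Table 1, footnote c). Section 7.3 gives paired tests for fitness measurements as a class and does not mention load lifted. The data list in section 10.4 includes repetitions, weight and load lifted for each exercise.

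**The concern.** A product that scales with repetitions and sets is a measure of work volume. It can stand in for intensity only if the set and repetition scheme stays fixed, and here the planned scheme changes between the calculation times. A change in the product then reflects the schedule as well as the participant.

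The risk is a reading in the wrong direction. In a study of high-load training, a falling main-lift figure could be taken as falling intensity when the participant is lifting more. A rising figure on other lifts could be taken as progress when only the repetition count changed. The part of the study exposed is the load-lifted half of exploratory objective 3.

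Two gaps add to this. The unit is unclear: Appendix III assesses strength by exercise but refers to weight by workout. Items with no recorded weight, such as the timed side plank, have no defined load.

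**Working it through.** The documents give no numerical volume load, so there is no stated figure to reproduce. The check applies the plan's own formula to its example schedule.

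**Inputs**
- Formula: load = weight × repetitions × sets (5.3, Appendix III).
- Times: week 3, then every 4 weeks, so about weeks 3, 7 and 11 (Appendix III). Counting from the end of week 3 gives about weeks 4, 8 and 12, which fall in the same blocks.
- Main lifts (5.3): 4x6 = 24, 4x4 = 16 and 4x2 = 8 repetitions per session.
- Other lifts (5.3): 3x10 = 30, then 3x12 = 36 from week 7.
- Growth in weight is not given. It is assumed to lie between 0% and +200%.

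**Main lifts.** For weight growth g since week 3:
- Load ratio at week 7 = (1 + g) × 16/24. Break-even weight is 24/16 = 1.5-fold.
- Load ratio at week 11 = (1 + g) × 8/24. Break-even weight is 24/8 = 3-fold.

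| Weight growth, week 3 to 11 | Load ratio, week 11 to week 3 |
|---|---|
| 0% | 0.33 |
| +20% | 0.40 |
| +50% | 0.50 |
| +100% | 0.67 |
| +200% | 1.00 |

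A participant whose weight doubles goes from 24W to 8 × 2W = 16W, a fall of 33%.

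To see how far a 3-fold rise is from what 1RM extrapolation alone would give, two equations are assumed, since the plan names none: A, 1RM = w(1 + r/30); B, 1RM = 36w/(37 − r). At unchanged 1RM, moving from 6 to 2 repetitions raises the weight from 0.8333 to 0.9375 of 1RM under A (ratio 1.125), or from 0.8611 to 0.9722 under B (ratio 1.129). The load ratio is then 1.125 × 8/24 = 0.375 or 1.129 × 8/24 = 0.376. Weight relative to 1RM rises while load falls by about 62%.

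**Lifts going from 3x10 to 3x12.** At unchanged weight the ratio is 36/30 = 1.20, a 20% rise from the scheme alone. Break-even weight is 30/36 = 0.833.

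**Workout total.** Take Day Two: the deadlift plus the three B lifts, with the band exercise left out. Assume equal B-lift weights and a week-3 deadlift weight k times each of them. The week-3 total is 24k + 90.
- All weights unchanged: the week-11 total is 8k + 108. For k = 1, 3, 5: 116/114, 132/162, 148/210, or +1.8%, −18.5%, −29.5%.
- 1RM up 25% on every lift, equation A: deadlift weight × 1.25 × 1.125 = 1.406; B-lift weight × 1.25 × 0.7143/0.7500 = 1.190. The week-11 total is 11.25k + 128.57. For k = 1, 3, 5: 139.8/114, 162.3/162, 184.8/210, or about +23%, 0%, −12%.

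Under the same assumption the main lift alone gives 1.406 × 8/24 = 0.469, a fall of 53%. The answer therefore depends strongly on the unit.

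**The case against.** The best reply is that nothing announced in the plan goes wrong. Intensity is not an endpoint. Objective 3 keeps strength and load lifted apart, and Appendix III also separates the run-in strength assessment from the later load calculation. The plan calls the product volume load and prints its formula, so a reader can see what is computed. It does not define intensity as a percentage of 1RM. The schedule is an example, and regimens are adjusted as they go.

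Most of this stands, and it limits the point to minor. It does not remove it. Section 5.3 still states a use, estimating intensity, for which the product fails whenever repetitions change, and the example shows planned changes in both directions. The example fixes the size; the direction problem follows from the formula.

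A reader might infer more than the documents support:
- *That relative intensity falls on the 3x12 lifts.* This would need weight to be reduced when repetitions rise. No reduction is stated; section 5.3 describes weight being increased once repetition goals are exceeded.
- *That load will be reported or tested as strength.* No section says so, and section 7.3 names no test of load. The first load calculation is at week 3, so there is no pre-programme value either.
- *That the sign is wrong in general.* The large falls are for single main lifts. Workout totals can rise, stay level or fall.
- *That strength is otherwise unmeasured.* Grip strength is measured separately.

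**Conclusion.** The concern holds as a minor point about an exploratory measure. Volume load is training volume and should not be labelled intensity, or left as the sole calculation under a strength heading without saying what it measures.

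The break-even figures follow directly from the example schedule: 1.5-fold weight by week 7 and 3-fold by week 11 for main lifts, and a 20% rise from the scheme alone for lifts going from 3x10 to 3x12. They apply to one exercise at a time and assume that the example is followed. The 1RM-based figures also assume one of two equations and sets at the repetition maximum. The totals assume relative weights that the plan does not give.

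The attendance endpoint, the sample size and grip strength are unaffected. Using load to guide progression during training is not questioned.

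**What to change.** Change the analysis wording and leave the regimen as it is.

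1. In section 5.3 and Appendix III, describe volume load as training volume, not as intensity or strength.
2. State that it is reported per exercise and descriptively, and that changes across different set and repetition schemes are not interpreted as changes in intensity or strength.
3. For any statement on exercise intensity or exercise-specific strength, use the stored weight per exercise, shown alongside the repetitions, or 1RM estimated by one named equation.
4. Exclude items with no recorded weight.
5. Keep grip strength as the strength measure at baseline, completion and 1 year.

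The cost is low, because weight and repetitions are already recorded (5.3) and on the data list (10.4). The downsides should be stated. Weights at different repetition numbers are only roughly comparable; in the example the main lifts use 6, 4 and 2 repetitions and never match. Estimated 1RM is approximate and valid only for sets near failure. A near-failure flag would help to identify those sets, but it is not on the data list, is optional, and is not needed for the fix.

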6. PATIENT ASSESSMENTS

Table 1: Participant Assessments

Assessment	Screening	Baseline Assessments (Prior to Program)	During Exercise Program	At Exercise Program Completion	1 Year After Exercise Program Completion
Consent	X				X ^f
History/Physical	X				
Weight, height, and BMI	X			X	X
Body Composition Assessment ^a		X		X	X
Resting Metabolic Rate Assessment		X		X	X

QOL and Exercise Forms ^b		X		X	X
Strength Assessment ^{c,d}		X	X	X	X
Mobility Assessment ^c		X		X	X
Compliance ^e			X		

- a To calculate lean and fat mass and percentages, and total energy expenditure (kcal/day) SOC
- b EQ-5D-5L, and Leisure-Time Exercise Questionnaire SOC
- c Functional Mobility Survey and Y-balance test, includes grip strength SOC
- d Will also occur periodically throughout program to adjust exercise regimen SOC
- e Attendance collected at each workout
- f Verbally reconsent to use SOC data for research purposes

6.1 Screening Assessments

An informed consent will be signed by the patient before any study enrollment and further workup ensues. Subject data to be collected from the medical record including retrospective care data, during the screening process including a complete history and outcome data from treatment and disease progression, all exercise information and questionnaires as well as assessments.

6.2 Study-Specific Assessment

a. Baseline Examinations

If not already collected during screening, baseline complete history and physical, weight, height, and BMI will be collected as SOC. In addition, baseline QoL forms, and the Leisure-Time Exercise Questionnaire that are SOC, will be administered. It will take 15-20 minutes to complete both questionnaires. All baseline assessments will be performed at the Exercise Oncology Center as per SOC, and must be collected within the 3 months prior to starting the exercise regimen. No laboratory draws for this protocol are required.

b. Baseline Metabolic, Body Composition, Strength, and Mobility Testing

Prior to initiation of the exercise regimen, each participant will undergo body composition analysis via an InBody 970. InBody testing is noninvasive and requires no ionizing radiation. The individual simply stands on the machine while holding handles. An ultrasound will also be used to measure muscle and adipose tissue thickness to provide additional metrics for body composition. This will be performed via a traditional ultrasound and software (BodyMetrix) will calculate

muscle mass, fat mass, and body composition metrics. More information is supplied in Appendix VI. Both also supply resting metabolic rate calculations. Functional movement assessments will be performed at this visit as well, and takes approximately 10 minutes.

Resting metabolic rate may also be assessed per SOC at this session via a VO2 Master device (VO2 Master Health Sensors Inc., British Columbia, Canada), where the individual will breathe into the device for several minutes at a time. The total test takes less than 15 minutes. The test is noninvasive and measures respiratory airflow and oxygen consumption in order to calculate resting metabolic rate. Alternatively, the InBody machine and ultrasound can be utilized to measure metabolic rate as well. Additional testing with this device is at the discretion of the staff as per SOC. Grip strength will be assessed via a Jamar Hand Dynamometer Grip Strength Measurement Meter bilaterally at the neutral position and with the arm of the head.

These tests are part of the SOC exercise regimen and workup and no additional costs will be associated with these procedures.

6.3 Exercise Period:

The exercise program will last three months. The initial exercise schema was developed by the PI and exercise personnel. Throughout the exercise program, participants will continuously be assessed via load lifted calculations and observations of exercise mechanics, both of which will impact increases in load and exercise difficulty during the program, as per SOC.

6.4 Follow-up Period:

There will be no follow-up once an individual completes the study.

6.5 Early Withdrawal of Subject(s):

If at any time the constraints of this protocol are detrimental to the patient's health and/or the patient no longer wishes to continue in the study, the patient will be removed from the protocol follow-up. In this event the reason(s) for discontinuation of study participation will be noted by the PI in the record. Data acquired up until that point will be retained for analyses.

There will be a SOC follow up assessment 1 year after the completion of the exercise program. The data from the SOC assessment will be used for research purposes.

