3 PROTOCOL SYNOPSIS

3.1 Purpose:

This protocol seeks to analyze patient outcomes of the standard of care, monitored group exercise regimen of high-load resistance training and functional exercises with compound movements under close supervision on women who have been treated for breast cancer.

Primary Objective

- 1 Determine safety and feasibility measured by exercise compliance.

Exploratory Objectives

- 1 Determine changes in functional mobility testing changes at baseline, throughout, post-exercise assessment and 1 year after exercise assessment.
- 2 Determine quality of life at baseline, throughout, and post- exercise assessment
- 3 Determine changes in strength and load lifted at baseline, throughout, post-exercise assessment, and 1 year after exercise assessment.
- 4 Determine changes in resting metabolic rate at baseline, throughout, post- exercise assessment, and 1 year after exercise assessment.
- 5 Determine changes in body composition at baseline, throughout, post- exercise assessment and 1 year after exercise assessment, including body mass, fat mass, fat-free mass, % fat, and % fat-free mass.

Hypotheses

In this study, we hypothesize that an observed exercise regimen utilizing high-load resistance training initiated during or after cancer treatment is safe and feasible in women and may improve functional mobility, body composition, and resting metabolic rate.

3.2 Background and Significance:

Obesity is a risk factor for both breast cancer and disease recurrence after treatment.¹ Furthermore, weight gain during and after treatment for breast cancer is associated with a higher risk of recurrence, distant metastases, and death.² Yet, most women gain significant weight during and after breast cancer treatment, potentially compromising outcomes.

Contrary to these findings, activity levels have been repeatedly associated with a lower risk of breast cancer incidence, improved outcomes after breast cancer treatment, and improved breast cancer-specific and overall survival.³ The majority of breast cancer survivors do not meet adequate daily activity level recommendations, potentially compounding issues with weight gain during and after breast cancer treatment.⁴ As a result, attempts are underway to both quantify and increase activity levels during treatment and survivorship.⁵ Furthermore, and based on these findings, several areas of

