3.5 Selection of Subjects and Sample Size:

Women ages 20-89 treated for ductal carcinoma in situ or invasive carcinoma will be considered for this trial.

The accrual goal is 43 subjects to achieve a sample size of 40 subjects, allowing for enrolled subjects who are unable to be complete the exercise program. Estimated accrual and completion time is approximately 2 years.

3.6 Duration of Study:

Subjects will be on study for an approximate 15 months, with the exercise program encompassing 12 weeks and an assessment following 1 year after the exercise program. Thereafter subjects will continue to be followed by the treating medical oncologist and/or radiation oncologist per standard of care (SOC) for follow up care but utilizing the data for research purposes.

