7.3 Analysis of Anthropometric, Metabolic, Fitness and QOL Measurements

All of the anthropometric, metabolic, fitness and QOL measurements are continuous variables. After assessing for normality, changes from baseline will be made using a paired t-test if the distribution is normal or by the Wilcoxon signed-rank test if the distribution is non-normal.

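### Baseline for body composition, metabolic rate, mobility, grip and questionnaires may be up to 3 months old at the first session, as long as the programme itself, and section 7.3 counts any movement in that gap as change from baseline

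*Combined protocol and SAP*

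**What the plan says.** Section 6.2a covers all baseline assessments and states that they "must be collected within the 3 months prior to starting the exercise regimen". Section 6.2b gives no tighter limit: "Prior to initiation of the exercise regimen, each participant will undergo body composition analysis via an InBody 970", with ultrasound, movement tests, resting metabolic rate and grip strength described alongside.

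Section 3.6 describes subjects as on study for about 15 months, "with the exercise program encompassing 12 weeks and an assessment following 1 year after the exercise program". Section 6.3 puts it as "The exercise program will last three months".

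For the analysis, section 7.3 says that "changes from baseline will be made using a paired t-test if the distribution is normal", with the Wilcoxon signed-rank test otherwise. It has no term for the time from baseline to first session, no repeat baseline and no sensitivity analysis. Section 3.4 describes a single-arm study.

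Two parts of the plan do not use this window. Section 5.3 and Appendix III take exercise-specific strength during the first two weeks of the programme and calculate load lifted from week three. The primary feasibility endpoint in section 7.2 is session attendance.

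**The concern.** A change from baseline is naturally read as the change over the exercise programme. Here it can also contain up to three months in which the woman was not yet exercising, and with one arm there is no comparison group to remove that part.

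The plan gives reason to expect movement in that period. Section 3.2 says that "most women gain significant weight during and after breast cancer treatment". Section 4.1 excludes women on active chemotherapy or immunotherapy but sets no minimum time since surgery, radiation or earlier chemotherapy, and hormonal therapy may continue. Weight, mobility and quality of life may all be shifting. Fat gain before session 1 would hide a benefit, while recovery of function after treatment would look like one. EQ-5D-5L asks about health on the day it is completed, so an answer from three months earlier does not describe a woman's state at the start.

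The gap can also differ between women, so change may span 12 weeks for one and about 25 for another. The data list in section 10.4 does not name the baseline date or the gap, so the plan does not ensure that a reader could see this.

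At stake is the interpretation of most of the exploratory results, including the improvements in mobility, body composition and metabolic rate that section 3.1 hypothesises.

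**Working it through.** The plan gives no figure for baseline drift, for the SD of change or for the gaps that occur. Its only calculated figure, the bound of 0.56 in section 7.2, concerns attendance and does not depend on baseline. The check is therefore of time shares, followed by illustrations on stated assumptions.

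**Inputs.** Maximum gap: 3 months (6.2a) = 3 × 365.25/12/7 = 13.04 weeks. Programme: 12 weeks (3.6). Late assessment: 1 year after the programme, taken as 52 weeks.

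**Gap against programme.** 13.04/12 = 1.09. If the programme is instead read as three months (6.3), the two are equal.

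**Share before the first session.** To completion, share = gap/(gap + 12). To 1 year, share = gap/(gap + 12 + 52).

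| Gap (weeks) | Share to completion | Share to 1 year |
|---|---|---|
| 0 | 0% | 0% |
| 2 | 2/14 = 14% | 2/66 = 3% |
| 4 | 4/16 = 25% | 4/68 = 6% |
| 8 | 8/20 = 40% | 8/72 = 11% |
| 13 (limit) | 13/25 = 52% | 13/77 = 17% |

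**What a shorter window leaves.** If drift were linear and continued through the programme, total drift would be proportional to gap + 12. Going from 13 weeks to 2 leaves 14/25 = 56% of it; going to 4 leaves 16/25 = 64%.

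**Illustration in kg (assumed rates).** At a background fat gain of 0.1 to 0.5 kg per month, a 3-month gap adds 0.3 to 1.5 kg to the measured change, and a half-month gap adds 0.05 to 0.25 kg.

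**Illustration for the paired t-test (assumed drift).** With n = 40, no exercise effect and a mean drift of d SDs of the change, the statistic is noncentral t with 39 degrees of freedom and noncentrality d√40. For d = 0.1, 0.2, 0.3 and 0.5, a nominal two-sided 5% test is significant 9.5%, 23.5%, 45.7% and 86.9% of the time. With n = 32 (the 20% dropout of section 7.2) the figures are 8.5%, 19.5%, 37.6% and 78.2%. These show sensitivity to drift; they do not estimate it.

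**Precision of a gap-adjusted estimate.** Regressing change on gap g, the estimate at g = 0 has standard error (s/√n) × √(1 + ḡ²/v), where s is the residual SD and ḡ and v are the mean and variance of the gaps. If gaps were spread evenly over 0 to 13 weeks (an assumption), ḡ = 6.5, v = 13²/12 = 14.08, ḡ²/v = 3.0 and the factor is √4 = 2. If the mean gap equalled its SD, the factor would be √2 = 1.41.

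**The case against.** The strongest reply concerns reach. A reader might infer that every exploratory objective is compromised. The documents do not support that: exercise-specific strength and load lifted start inside the programme, so the strength objective is exposed only through grip strength. Nor is the feasibility result touched, since attendance uses no baseline measurement and no success criterion or sample size rests on section 7.3. This part of the reply stands in full.

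A second reply is that three months is a ceiling. The documents do not say how long the gaps are, and standard practice at the centre may keep them short. That also stands. The 52% is a share of time in the worst case; a reader might take it to mean that half of any reported change is drift, and nothing in the documents shows that.

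A third is that a shorter window does not substitute for a control group. On the linear assumption, more than half the drift remains. This is correct and limits the benefit, but the part that lies before session 1 is the avoidable part.

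Finally, the study is built on standard-of-care data. Compulsory repeat testing would add research procedures, including another overnight fast for InBody, and would unsettle the statement in section 6.2 that no additional costs arise. No particular cut-off such as 14 days has support in the documents. These are good reasons against mandatory repeats. They do not count against scheduling the one visit nearer the start, since the protocol already sets a window for these assessments.

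**Conclusion.** The point holds as a limited, cheaply reduced weakness in the exploratory analyses. The permitted baseline window is as long as the programme, nothing elsewhere narrows it, and the analysis does not allow for it. It affects body composition, resting metabolic rate, mobility, grip strength, EQ-5D-5L and Godin. At the limit, 52% of the interval to completion and 17% of the interval to 1 year precede exercise.

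Those shares follow from the stated window and programme length. The size and direction of any bias do not: they depend on actual gaps and drift rates that the documents do not give, and different outcomes could be biased in opposite directions. Confidence is high about the rule and its worst case, and low about its practical effect.

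**What to change.** 1. **Section 6.2a, women not yet assessed.** Schedule the single baseline visit close to session 1, for example within 2 to 4 weeks. The figure is a matter of judgement; at 4 weeks the pre-programme share to completion is at most 25%, and at 2 weeks 14%. Do not require repeat testing.
2. **Section 10.4, all women.** Add the date of each baseline assessment and of the first session. Attendance is already collected at each workout, so the second should be to hand. Report the distribution of the gap.
3. **Section 7.3.** Keep the paired analysis and add a sensitivity analysis, using all participants, that regresses change on the gap and gives the estimated change at a gap of zero, with its interval. A subset with short gaps is less useful because, out of about 40 women, it could be very small.
4. **Reporting.** State that drift during the programme cannot be separated from the effect of exercise in a single-arm study, that the regression assumes linear drift, and that women with longer gaps may differ in other ways.

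The cost is a short amendment with IRB approval, some rescheduling, and wider intervals in the sensitivity analysis. These could be about twice as wide if gaps are spread evenly from zero, which is why it should support the paired analysis and not replace it.
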